**PARTNERS HUMAN RESEARCH COMMITTEE
PROTOCOL SUMMARY**

Answer all questions accurately and completely in order to provide the PHRC with the relevant information to assess the risk-benefit ratio for the study. Do not leave sections blank.

PRINCIPAL/OVERALL INVESTIGATOR

[name], MSc

PROTOCOL TITLE

mFOCUS (multilevel FFollow-up of Cancer Screening), RCT

FUNDING

NCI (U01CA225451)

VERSION DATE

January 6, 2023

SPECIFIC AIMS

Concisely state the objectives of the study and the hypothesis being tested.

Specific Aim 1: To evaluate the effectiveness of the system, team and individual components of mFOCUS vs. standard care by conducting a 4-arm cluster randomized controlled trial (RCT) of individuals who are due for follow-up of an abnormal cancer screening test. Standard care consists of well-characterized existing decision support and systems for follow-up in these three participating primary care networks and their affiliated integrated delivery systems (Brigham and Women's Hospital and Massachusetts General Hospital, both members of Partners HealthCare System, Massachusetts's largest integrated health care delivery system, and Dartmouth Hitchcock Health, the largest health care provider in New Hampshire). The primary outcome will be whether an individual receives follow-up, defined based on the type of screening abnormality and organ type, within 120 days of becoming eligible for mFOCUS. Secondary comparisons will assess multi- and cross-level (individual, team, system) outcomes. Because the Coronavirus pandemic impacted access to health care, we will also assess whether an individual receives follow-up, defined based on the type of screening abnormality and organ type, within 240 days of becoming eligible for mFOCUS. The study design will allow us to examine the marginal effectiveness of system, team and individual-level enhancements, and exploratory analyses will address subgroups defined by race/ ethnicity, socioeconomic status and cancer type.

Hypothesis: mFOCUS will significantly increase the proportion of individuals who receive follow-up testing, thereby reducing time to follow-up vs. standard care.

Specific Aim 2: To evaluate facilitators and barriers to the Reach, Adoption, Implementation and Maintenance of mFOCUS at participating primary care practice sites affiliated with three primary care networks The impact of any intervention depends on its ability to be implemented in clinical practice.

Hypothesis (Reach): Individuals who are due for follow-up can be reached by mFOCUS irrespective of patient sociodemographic characteristics and "severity" of the screening result. Patient surveys will be used to examine barriers and facilitators.

Hypothesis (Adoption, Implementation, and Maintenance): mFOCUS will be *adopted* across providers/ practices and consistently *implemented*. Provider and system-level surveys will be used to examine barriers and facilitators to adoption, implementation and maintenance.

NOTE: This protocol involves patients who receive care at Partners (MGH and BWH) as well as Dartmouth. Dartmouth is the relying site on the Partners IRB review a SmartIRB reliance agreement has been put in place

BACKGROUND AND SIGNIFICANCE

Provide a brief paragraph summarizing prior experience important for understanding the proposed study and procedures.

In the United States (US), most cancer screening is initiated in primary care settings but requires care transitions with other providers who either perform the test or evaluate the result. Screening benefits are only realized through timely follow-up of abnormal breast, cervical, colorectal and lung screening results. Incomplete follow-up represents an ongoing challenge as the initial screening event transitions to diagnostic evaluations involving complex interactions among patients, primary care providers (PCPs), and specialists.

Our recent study within the NCI-funded Population-Based Research Optimizing Screening through Personalized Regimens (PROSPR) consortium reported significant rates of screening abnormalities that required additional evaluation, including; 11% of breast cancer, 8% of cervical and 5% of fecal occult blood test (FOBT)/ fecal immunochemical test (FIT) screens, consistent with other studies. The abnormality rates for colonoscopy screening (~20% adenomas) and lung cancer screening with low dose computed tomography (LDCT)'s are also high (~25%). Our work also demonstrates wide variation in follow-up rates across primary care clinics, that differ by cancer type as well as the "severity" of the screening abnormality (5 – 95% with an average of ~ 50% overall). Apart from the

legislated requirement for radiologists to follow-up abnormal mammograms, responsibility for comprehensive screening follow-up falls to the ordering provider, typically a primary care provider (PCP). Unfortunately, few PCPs/primary care practices have systems to track abnormalities and promote follow-up. PCPs face the challenge of responsibility for managing the diagnostic evaluation for populations of patients for each of these cancers, each with differing requirements and timeframes for completion.

Barriers to follow-up of “abnormal screens” exist at individual patient and provider levels as well as at patient’s care team and health system levels. Providing high-quality care for abnormal screens requires establishing new processes to systematically identify abnormal results, notify patients and providers, address barriers, and track completion of the diagnostic work-up. We propose to develop, test and disseminate a health information technology (IT)-enabled, multilevel, stepped care intervention grounded in primary care, mFOCUS (multilevel FOllowup of Cancer Screening) for abnormal breast, cervical, colorectal and lung screens. Comprehensive intervention to promote follow-up needs to be based in primary care as PCPs holistically approach each patient’s needs and coordinate care among specialists. Key mFOCUS components include: system design to promote identification/tracking using an electronic health record (EHR)-integrated population management platform with education to promote culture change around the management of abnormal screens; use of individual patient and PCP reminders and tools; and a stepped-care team-level enhancement with increasing intensity of contact (i.e., administrative support and patient navigation).

RESEARCH DESIGN AND METHODS

Briefly describe study design and anticipated enrollment, i.e., number of subjects to be enrolled by researchers study-wide and by Partners researchers. Provide a brief summary of the eligibility criteria (for example, age range, gender, medical condition). Include any local site restrictions, for example, “Enrollment at Partners will be limited to adults although the sponsor’s protocol is open to both children and adults.”

Specific Aim 1: To evaluate the effectiveness of the system, team and individual components of mFOCUS vs. standard care by conducting a 4-arm cluster randomized controlled trial (RCT) of individuals who are due for follow-up of an abnormal screen.

Inclusion criteria: Individuals who have an abnormal screen that is due for follow-up including:

- Breast: women 40-80 years with an *incident* (i.e., newly detected) abnormal screening mammogram or digital breast tomosynthesis (DBT) exam.
- Cervical: women 21-65 years with an *incident* abnormal screening Pap.

- Colorectal: adults 40-80 years with an abnormal screen, including *incident* FOBT/ FIT, or *prevalent* colonoscopy. Because of the long periods of time required for follow-up of colonoscopies, we will look back over a 5-year period and will therefore find *prevalent* abnormalities that become due for follow-up.
- Lung: adults 55-80 years, current and former smokers, with an *incident* abnormal LDCT result.

Definition of the specific screening abnormalities and timing of diagnostic evaluation are based on our prior work, expert opinion, and the literature. Need for follow-up will be determined by the lack of an appropriate clinical test within the specified time as documented in the EHR.

Exclusion criteria: We will exclude patients who: 1) are not English or Spanish-speaking, or 2) have had prior cancer of the organ for each screening test (i.e., women with prior breast cancer will not be tracked for breast cancer screening abnormalities) as these individuals may have non-standard follow-up care recommendations.

Intervention Design and Randomization Scheme. We will perform a 4-arm cluster RCT with randomization done at the practice-level, across the participating practices. We have chosen this level of randomization as it would be logistically complicated for the practices to have different patients randomized to different intervention components (i.e., reduced contamination). While we have received the approval of the primary care network leadership of the participating networks and have discussed the study with practice leadership, practices will be given the opportunity to opt-out of the study before practices are randomized. Randomization will be stratified based on: (1) practice size, (2) percent female, and (3) percent of patients on Medicaid as a marker for socioeconomic status.

The 4-arm design will allow us to compare “standard care” (Arm 1) to three intervention arms that represent the sequential/ stepped addition of: (Arm 2) a system-level, visit-based intervention consisting of PCP facing reminders deployed when a patient is overdue for follow-up (health maintenance reminders; automated problem list additions); (Arm 3) the addition of a population-based intervention with study staff administration of the patient and PCP facing reminders deployed when a patient is overdue for follow-up regardless of whether they come in for a visit (e.g. bulk In-Basket messaging to the PCP, Patient Gateway reminders or letters, a brief phone call or voice message for the patient); and (Arm 4) the addition of a team-level intervention including phone calls from an outreach coordinator and a patient navigator. Part of the role of the Patient Navigator will be to assess a patient’s social determinants of health. If the patient has any needs the patient navigator will use “Aunt Bertha” an online platform to help patients find social services in their area. Patients in Arm 1 will receive the usual care provided by their PCP. Given our stepped care approach, this randomization

scheme will allow us to compare the cumulative addition of each level of intervention to standard care as well as the marginal effect of each additional level to the prior group. This design allows us to evaluate changing the responsibility for “opportunistic” follow-up, typically by the PCP at the time of a visit (Arm 1), to a systematic, multilevel approach, examining the cumulative and marginal effects of each subsequent level of intervention. In addition to the multilevel components, the individual- and team-level engagement algorithm will take a “stepped care” approach with increasing level of intensity of engagement.

Recruitment and Enrollment. Key organizational components of the study will involve:

(1) Practice and Provider Engagement. We have obtained support of network leadership for the study. Investigators have/ will attend practice meetings at intervention sites to integrate work flow with practice routines and educate staff about the study and its procedures. PCPs will not be required to do recruitment; identification of eligible patients will be done centrally using the IT platform described above. We therefore anticipate a high level of practice and PCP participation since the intervention does not constrain usual practice, but adds additional systems beyond those currently available. As noted above, practices and providers will be given the opportunity to opt-out of the study before practices are randomized.

(2) Patient Identification and Enrollment. The mFOCUS platform will incorporate algorithms to identify eligible patients and patient-practice attribution. All patients will remain under the direction of their personal PCP/ practice and the intervention components will facilitate the delivery of care in addition to the current standard of care.

We plan to enroll 3324 eligible participants (approximately 831/ arm – as randomization will be done at the practice level the arms will not be the same size) across the 3 participating primary care networks (BWH, MGH, and Dartmouth). We anticipate that recruitment will be somewhat higher at BWH and MGH than Dartmouth as the networks are bigger. Because randomization will be done at the practice level, we will not be able to recruit exactly 3324 individuals (patients will be in process of recruitment since they will be recruited in batches) – this is the number suggested by our sample size calculation. We anticipate that this calculations will need to be updated due to the impact of COVID-19 and that our recruitment number will be higher because of the back log of testing that will occur as hospitals reopen for screening procedures. We anticipate that we could possibly enroll up to 9,000 eligible patients at MGH/BWH, and 12,000 eligible patients study wide. We will not exceed recruitment of 12,000 eligible individuals. Due to the way our IT system is configured, we anticipate that we could review up to 20,000 patient charts study wide. Not all of the patient charts reviewed will be deemed eligible.

Any patient contact (outreach coordinator, patient navigator) will be done by staff at the respective patient care sites (Partners staff will contact Partners' patients and Dartmouth staff will contact Dartmouth patients). Dependent upon randomization, patients will receive a patient gateway message (if patient has an account) or mailed letter and a phone call from a study coordinator. Patients in study arm 4 will receive patient navigation, which may involve multiple contacts by phone and/or the by a telehealth Partners approved platform.

(3) Surveys: Some of the outcomes of the study will be measured by PCP and patient surveys:

PCP Surveys: We developed brief, self-administered survey instruments to be administered to PCPs just before the trial is launched and 3 months after recruitment ends.

PCPs will be sent an introductory email from the clinical director of each primary care network. This will be followed by an email from the study investigators that explains the study purpose and opportunities to opt out/ participate of the survey. The second email will include a unique url for the PCP to use to connect to a RedCap version of the survey. PCP surveys will be administered using RedCap (up to 5 email contacts with a RedCap link over 4 weeks).

Patient surveys: We will randomly sample 15% of participants. Patient surveys will be administered 4-12 weeks after their individual follow-up period has been completed, so surveys will be conducted throughout the enrollment period. Patients will be sent an introductory letter from the clinical director of each primary care network paired with a letter from the study investigators that explains the study purpose and opportunities to opt out/ participate of the survey. The second letter will include a unique url/QR code for the patient to use to connect to a RedCap version of the survey. If patients do not opt-out within 2 weeks or complete the survey using the RedCap link provided in the letter, they will be contacted by phone and asked to complete the survey by phone or RedCap. If the patients opt for the later, they will be asked for permission to receive the survey link via un-encrypted email (and asked for the email where they would like to receive it).

Summary of primary and secondary outcome measures

Measures (data source)

Primary outcome: Completion of follow-up within 120 days of eligibility for mFOCUS (EHR/ claims)

Secondary outcomes:

Completion of follow-up within 240 days of eligibility for mFOCUS (EHR/ claims)

Patient-Reported Assessment of:

Individual-PCP: Satisfaction with care provided by PCP

Care Team: Satisfaction with care provided by care team

System: Receipt of reminder letters, calls, or emails

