# of days to completion of required diagnostic evaluation (EHR/ claims)	
Satisfaction with follow-up care (patient survey)	
Knowledge of test result and need for follow-up (patient survey)	PCP-Reported Assessment of:
Satisfaction with ability of patients to get timely follow-up (PCP survey)	Individual-Patient: Patient understanding of need for follow-up
Time required for management (PCP survey)	Care Team: Satisfaction with coordination of care
	System: Satisfaction with IT functionality to support follow-up

Analysis Plan/ Sample Size. Our primary analysis will be intention-to-treat (ITT). All eligible, enrolled patients will be part of the ITT cohort. We expect that a small number of patients may change primary care clinics within our systems. These individuals will be evaluated according to their initial intervention status. Prior to analysis, all data will be examined for accuracy, logical consistency and missing data. We expect complete data for intervention status and our outcomes. We will use multiple imputation, using the MI procedure in SAS, to account for any missing values of covariates. Through the stratified randomization we will attempt to balance patient, provider and practice characteristics between study groups. However, since randomization occurs at the practice level, we will be cautious and still compare the patient, provider and practice characteristics using Fisher exact tests, t-tests and Wilcoxon tests as appropriate to the covariate distribution. Any characteristics that show substantial clinical or statistical difference ($p < .05$) will be entered into the regression model and retained as covariates if they alter the effect estimate of the intervention by $> 20\%$.

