The primary analysis model will be a random effects logistic regression, implemented through the SAS Glimmix procedure. Timely follow-up (yes/no) will be the patient-level outcome and random effects for practice and physician will allow for exchangeable correlation between patients seen within the same practice and by the same physician. The primary fixed predictors will be 3 indicator variables representing the 3 intervention arms and we will use a global likelihood ratio test to compare the 4 study arms. If the global test is significant ($p < 0.05$), we will compare the intervention arms to the control group (our primary comparisons with a Bonferroni-adjusted significance level of 0.0167) and to each other (secondary comparisons). Comparisons to the control arm will capture the cumulative effects of the interventions, while comparisons between the intervention arms will capture the marginal effects of each level of intervention. We will include covariates for the type of cancer, level of initial screening abnormality, and any patient, provider or practice characteristics which are identified as confounders.

Results will be presented as adjusted follow-up rates, with 95% confidence intervals, calculated using marginal standardization.

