In discussions (but not in the protocol), there was interest in exploring how COVID affected the outcome, in the sense that patients who became eligible when COVID was more prevalent (and elective care was less available) may have taken longer to have follow-up. Because this is a complicated topic and will distract from the main randomized results, it was decided to save such analyses for a subsequent manuscript. The current manuscript will simply adjust (through indicator variables) for 3-month time windows. Since COVID peaked in different areas at different times, these indicator variables will be included as interactions with study site (Boston versus Dartmouth).

Contents:

1. Exhibit 1: Figure 1: Consort Diagram
2. Exhibit 2: Table 1: Baseline Characteristics, by Arm
 - a. Patient characteristics
 - i. Sex
 - ii. Age
 - iii. Race/Ethnicity
 - iv. Primary insurance
 - v. Primary language
 - vi. Marital status
 - vii. Comorbidities
 - viii. Number of PCP visits in prior year
 - ix. Number of no show visits in prior year
 - x. Type of cancer
 - xi. Severity of screening abnormality
 - xii. Rurality (distance or population)
 - xiii.
 - b. PCP characteristics (from protocol; none currently in the prototype table):
 - i. Sex
 - ii. Provider type (MD/ DO, NP/ PA, other)
 - iii. Specialty
 - iv. Panel size (not risk adjusted)

- c. Clinic characteristics (from protocol; none currently in the prototype table):
 - i. Location (hospital; community health center)
 - ii. Visit volume at time of randomization
 - iii. Patient mix (% female; % Medicaid) at time of randomization

- 3. Exhibit 3: Table 2: Overall Primary (120 day completion) and secondary (240 day) outcome analyses
Intent-to-Treat and Modified Intent-to-Treat;
“Unadjusted” and Adjusted
 - a. Presentation: Data will be shown by arm, both ITT and mITT, both adjusted and “unadjusted”
 - i. The overall global p-value (<0.05) for the adjusted ITT analysis will be shown. If the global test is significant, then three pairwise tests (each arm against control/Arm 1) looking for $p<0.0167$.
 - ii. All other analyses and comparisons will be based on 95% confidence intervals

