 - b. Primary and secondary analyses: SAS Proc GLIMMIX with the patient as the unit of analysis and a binary outcome (completed/not completed). All models (including “unadjusted”) will include random effects for practices and physicians. All models (including “unadjusted”) will include fixed effects for type of cancer. All models (including “unadjusted”) will include indicator variables for time (calendar month), along with interaction terms with site (Boston versus Dartmouth).
 - i. Unadjusted analysis: The model above will include random effects for practices and physicians, fixed effects for cancer types, fixed effects and interactions for calendar month and study stie, and indicator variables for Arms 2, 3, and 4.

 - ii. Adjusted analysis: The covariates from 2 above will be added individually to the model. Any that are significant at $p<0.05$ and change the coefficient of any of the 3 indicators for treatment arm by $>20\%$ will be retained in the model as confounders. (Type of cancer and calendar month will be retained in the model regardless of significance or confounding.) Adjusted completion rates will be calculated by marginal standardization and presented in the Table.

- 4. Exhibit 4: Figure 2: Forest plot with subgroup analyses for the primary (120 day completion) outcome

Intent-to-Treat
Adjusted only

- a. Presentation: Data will be shown by subgroup as an odds ratio (versus the control arm 1) with 95% confidence interval; ITT; adjusted only
 - i. P-values for interaction will be presented
 - ii. All other comparisons will be based on 95% confidence intervals
- b. Subgroup analyses: SAS Proc GLIMMIX with the patient as the unit of analysis and a binary outcome (completed/not completed). All models will include random effects for practices and physicians. All models will include fixed effects for type of cancer and calendar month.
 - i. Subgroups (each set analyzed separately):
Type of cancer (breast; cervical; CRC; lung)
Severity of abnormality (low; medium; high)
 - ii. Adjusted analysis: The model above will include random effects for practices and physicians, fixed effects for cancer types and calendar month, indicator variables for Arms 2, 3, and 4, indicator variables for the subgroups, and interaction terms for the arms-by-subgroups.
A global test for effect modification will be run and reported. However, regardless of significance, a separate “unadjusted” model will be run for each subgroup.

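### The stratification factors are not required in any model, and the 20% change-in-coefficient rule will usually drop them; if they predict follow-up, power is forgone

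*Combined protocol and SAP*

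**What the plan says.** **Randomisation.** Protocol, Intervention Design and Randomization Scheme: "Randomization will be stratified based on: (1) practice size, (2) percent female, and (3) percent of patients on Medicaid". The Analysis Plan/ Sample Size section gives the purpose: "Through the stratified randomization we will attempt to balance patient, provider and practice characteristics between study groups".

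**Protocol selection rule (Analysis Plan/ Sample Size).** Characteristics that differ between arms, clinically or at p < .05, "will be entered into the regression model and retained as covariates if they alter the effect estimate of the intervention by" more than 20%. The primary model always carries type of cancer and level of abnormality. Beyond these it admits "any patient, provider or practice characteristics which are identified as confounders".

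**SAP selection rule (item 3.b.ii).** Candidates are added one at a time and kept if they are significant at p < 0.05 "and change the coefficient of any of the 3 indicators for treatment arm by" more than 20%. The only exemption is this: "Type of cancer and calendar month will be retained in the model regardless of significance or confounding". The calendar-time terms enter with site interactions (Boston versus Dartmouth).

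**Candidate list (SAP Exhibit 2, clinic characteristics).** It contains "Patient mix (% female; % Medicaid) at time of randomization" and "Visit volume at time of randomization". Practice size as such is not listed; visit volume is the nearest item.

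**Where it bites.** SAP item 3.a.i takes the global test from the adjusted ITT analysis, which is the model that this selection produces. All models have random effects for practice and physician.

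**The concern.** Stratifying makes the arms alike on the stratification factors, and a factor that is balanced across arms hardly moves an arm coefficient when it is added. A rule that keeps a covariate only if it moves that coefficient therefore tends to discard these factors because the stratification worked. The second conditions do not help. The protocol's baseline-difference screen is one more test that a balanced factor fails, and the SAP's p < 0.05 is required in addition to the 20% change, not instead of it.

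Stratification reduces the true sampling variance of the arm contrasts by whatever the factors explain. A model without the factors leaves that variance in the practice random effect and reports a standard error as if the reduction had not occurred. With at most 44 practices (Recruitment Procedures), between-practice variance is a large part of the error, so the precision that the design bought may not be used.

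**Working it through.** **Inputs from the documents.** N = 3324, about 831 per arm; at most 44 practices; 80% power for an 11-point difference; 0.0167 per comparison with control; average follow-up of about 50% (Background).

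**Assumptions.** Control rate 50%, two-sided tests, equal practice sizes (m = 3324/44 = 75.5), three binary factors giving 8 strata, permuted blocks of 4, no physician effect. ICC and R2 are not given and are varied.

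**1. The plan's own figure.** For 50% versus 61% at 0.0167 and 80% power without clustering,

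n = [2.393·√(2·0.555·0.445) + 0.842·√(0.25 + 0.2379)]² / 0.11² ≈ 426 per arm.

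The plan has 831. The gap implies a design effect of 831/426 = 1.95 and an ICC of about 0.95/75 ≈ 0.013. The calculations below use 0.0126. Neither quantity is stated, so 3324 can be neither confirmed nor refuted.

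**2. Overstatement of the standard error.** On a scale with total variance 1, without the factors:

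reported/true SE = √{[ICC + (1−ICC)/m] / [ICC(1−R2) + (1−ICC)/m]}.

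At ICC 0.0126, (1−ICC)/m = 0.9874/75.5 = 0.01308. For R2 = 0.50 the ratio is √(0.02568/0.01938) = 1.15.

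| R2 | 0 | 0.10 | 0.25 | 0.50 | 0.75 |
|---|---|---|---|---|---|
| SE ratio, ICC 0.0126 | 1.00 | 1.03 | 1.07 | 1.15 | 1.26 |

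At ICC 0.05 and R2 = 0.50 the ratio is 1.29.

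**3. Power and level under the SAP rule.** Practice-level linear models were simulated, 4,000 trials per scenario, with an 11-point effect in every intervention arm. Each factor was tested singly for p < 0.05 and a change above 20% in any arm coefficient.

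| ICC | R2 | Power, SAP rule | Power, factors forced in | Type I error, SAP rule (nominal 1.67%) |
|---|---|---|---|---|
| 0.0126 | 0 | 76.1% | 75.1% | 1.65% |
| 0.0126 | 0.25 | 77.2% | 81.3% | 1.27% |
| 0.0126 | 0.50 | 78.6% | 87.5% | 0.97% |
| 0.0126 | 0.75 | 79.5% | 92.7% | 0.75% |
| 0.03 | 0.50 | 50.5% | 70.8% | not tabulated |

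With the factors forced in, type I error at ICC 0.0126 was 1.6 to 1.8%. At ICC 0.0126 and R2 from 0.25 to 0.75, the rule kept on average only 0.02 to 0.06 of the three factors.

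Retention also depends on the effect itself, because a percentage change in a coefficient near zero is easily large. At ICC 0.05 and R2 = 0.50, the rule kept 1.72 factors on average under the null and 0.40 under an 11-point effect. The rule is thus least likely to keep the factors when the intervention works.

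**4. Check in a logistic model.** Random-intercept logistic models (up to 400 trials per scenario, Wald tests, ICC 0.0126, 11-point effect) gave power without versus with the factors of 82.8% vs 83.8% (R2 = 0), 84.0% vs 88.0% (0.25), 83.5% vs 92.5% (0.50) and 83.8% vs 95.0% (0.75). The direction is the same. Part of this gain is artificial: with the factors in at R2 = 0.25, the model SE was 0.119 against an empirical 0.129. Wald type I error with the factors in ranged from 1.5% to 3.5% over the null scenarios. Without the factors at R2 = 0 it was also 3.3%. The excess therefore comes from having few practices, not from adding the factors.

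**The case against.** The strongest reply is that none of this is certain.

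- **Dependence on R2.** If the factors do not predict follow-up between practices, forcing them in costs about one point. At R2 = 0.10 the gain is only about 2 points. In the logistic model at R2 = 0.25 the SE without the factors (0.132) was close to the empirical SE (0.130). This stands, so the point must be stated conditionally.
- **Terms already in the model.** Type of cancer and calendar time by site are in every SAP model. Breast and cervical eligibility is limited to women, so type of cancer may absorb part of any percent-female effect. This stands: the R2 that matters is what remains after those terms.
- **Larger enrolment.** The protocol allows up to 12,000 patients, or 272.7 per practice. At ICC 0.0126 the design effect is then 1 + 271.7 × 0.0126 = 4.42, and power for 11 points is about 95% without the factors. Little absolute power would be left to gain. The SE overstatement at R2 = 0.50 would nevertheless rise from 15% to 28%, so the intervals would be proportionally wider than they need be.

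Two stronger readings are tempting. A reader might infer that the trial falls short of its planned 80%. Nothing shows that the sample-size calculation took credit for stratification, and at the implied ICC, power under the rule did not fall below its R2 = 0 value. A reader might also infer bias or false-positive risk from omitting the factors. The error runs the other way: randomisation keeps the arm comparison unbiased, and type I error falls below nominal.

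**Conclusion.** The omission is clear from the text: three factors define the randomisation strata, no model must contain them, and the retention rule works against them. The consequence is conditional. If the factors predict follow-up between practices, the analysis is conservative and forgoes power: about 4 points at R2 = 0.25 and 9 points at R2 = 0.50 with ICC 0.0126, and about 20 points at R2 = 0.50 with ICC 0.03. If they do not, nothing is lost by leaving them out, and forcing them in costs about 1 point. These figures rest on an assumed ICC and R2, equal practice sizes and binary strata. The protocol describes wide variation in follow-up across clinics and chose Medicaid share as a socioeconomic marker, so some prognostic value is plausible, but the documents do not quantify it.

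The imbalance between a small possible cost and a larger possible gain justifies the change. It is a should-fix, not a threat to validity.

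**What to change.** In the protocol's Analysis Plan/ Sample Size section and SAP item 3.b, name practice size, percent female and percent Medicaid, coded as used in the randomisation, as fixed effects in the primary and secondary models. Retain them on the same terms as type of cancer, whatever their p-value or effect on the arm coefficients. Use the size variable from the randomisation; visit volume serves only if it was that variable. Carry the terms into the Cox model, which the SAP already ties to the logistic model's covariates.

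Specify a small-sample degrees-of-freedom correction for the arm tests. With at most 44 practices and 4 arms there are 40 practice-level degrees of freedom, and three binary factors leave 37.

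The factors need not be forced into every stratified subgroup model, where the SAP already limits covariates by sample size. Network is not among the listed stratification factors, so this point gives no reason to recode site.

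The protocol records that the study has ended. If the primary analysis has already been run as planned, keep it and report the stratum-adjusted model as a labelled sensitivity analysis.

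The cost is a sentence or two of wording and about 3 to 4 practice-level degrees of freedom. The data are already held.
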